### 3.1.1. Study Schema

## 4. SUBJECT SELECTION

### 4.1. Inclusion Criteria

To be enrolled in the study, each potential subject must satisfy all of the following inclusion criteria:

1. Pathologically confirmed:
  - NSCLC (adenocarcinoma or squamous-cell carcinoma) or
  - Breast cancer (HER2 positive [by FISH or IHC. See [Section 1.2](#) for definition] or triple negative) or
  - Pancreatic cancer (adenocarcinoma)

2. For Phase 2 only: Provision of a fresh tumor biopsy or an available archival tumor sample processed as formalin-fixed paraffin embedded (FFPE) taken within 3 months, and after the most recent treatment with the following exception:
  - For locally advanced pancreatic cancer, a fresh biopsy is not required if the tumor is inaccessible or the procedure places the subject at a safety risk.
  - No more than 10 subjects with locally advanced pancreatic cancer will be enrolled in the study without a biopsy.
3. Radiographically or clinically documented relapsed or refractory disease (Stage III or IV): Subjects with NSCLC or pancreatic cancer must have relapsed or refractory disease and must have failed at least 1 prior appropriate systemic first-line treatment regimen. Subjects with epidermal growth factor receptor (EGFR) mutation-positive NSCLC must have received an EGFR inhibitor and subjects with NSCLC that is anaplastic lymphoma kinase (ALK)-positive must have received an ALK inhibitor. Subjects with breast cancer must have relapsed or refractory disease and must have failed at least 2 prior appropriate systemic regimens.
4. One or more disease lesion on CT/MRI scan or by physical examination (if the lesion is not assessable by CT/MRI) that is measurable (ie, superficial soft tissue lesions, skin lesions, etc.) per RECIST 1.1 guidelines.
5. Adequate hematologic function independent of transfusion and growth factor support for at least 7 days prior to screening, with the exception of pegylated G-CSF (pegfilgrastim) and darbepoetin which require discontinuation at least 14 days prior to screening defined as:
  - Absolute neutrophil count (ANC)  $>1500 \text{ cells/mm}^3$  ( $1.50 \times 10^9/\text{L}$ )
  - Platelet count  $>100,000 \text{ cells/mm}^3$  ( $100 \times 10^9/\text{L}$ )
  - Hemoglobin  $>9.0 \text{ g/dL}$
6. Adequate hepatic and renal function defined as:
  - Serum aspartate transaminase (AST) or alanine transaminase (ALT)  $\leq 2.5 \times$  upper limit of normal (ULN) for subjects without liver metastases and  $\leq 3.5 \times$  ULN for subjects with liver metastases
  - Bilirubin  $\leq 1.5 \times$  ULN (unless bilirubin rise is due to Gilbert's syndrome or of non-hepatic origin)
  - Creatinine  $\leq 2.0 \times$  ULN and Creatinine Clearance  $\geq 40 \text{ mL/min}$  (Cockcroft-Gault or 24-hour creatinine clearance collection)
7. Prothrombin time (PT)/International normalized ratio (INR)  $< 1.5 \times$  upper limit of normal (ULN) and partial thromboplastin time (PTT)/ activated partial thromboplastin time (aPTT)  $< 1.5 \times$  ULN
8. Men and women  $\geq 18$  years of age
9. Eastern Cooperative Oncology Group (ECOG) performance status of 0 or 1
10. Female subjects must either be of non-reproductive potential (ie, post-menopausal by history:  $\geq 60$  years old and no menses for  $\geq 1$  year; OR history of hysterectomy; OR history of bilateral

tubal ligation; OR history of bilateral oophorectomy). Female subjects of reproductive potential must have a negative serum pregnancy test upon study entry.

11. Male and female subjects of reproductive potential who agree to use highly effective methods of birth control (eg, condoms, implants, injectables, combined oral contraceptives, some intrauterine devices [IUDs], complete abstinence, or sterilized partner) during the period of therapy and for 90 days after the last dose of study drug (see [Appendix 8](#)).
12. Men must agree to not donate sperm and a woman must agree to not donate eggs (ova, oocytes) for the purposes of assisted reproduction during or for 3 months after the last dose of either drug.

#### **4.2. Exclusion Criteria**

To be enrolled in the study, potential subjects must meet **NONE** of the following exclusion criteria:

1. Subjects with tumors of mixed small cell and NSCLC histology
2. Central nervous system (CNS) involvement of disease except as follows: Subjects with previously treated CNS metastases that are adequately treated with whole brain radiotherapy (+/- surgery), that are neurologically stable, and do not require corticosteroids (of any dose) for symptomatic management for at least 14 days prior to first dose of MEDI4736 plus ibrutinib. In addition, there must be no clear evidence of radiographically active disease for at least 90 days prior to enrollment.
3. Anti-tumor therapy (chemotherapy, antibody therapy, immunotherapy, biologic-based therapy, molecularly- targeted therapy, radiation therapy or investigational agent) within 21 days of study Day 1 (six weeks for nitrosureas, mitomycin C, or antibody or molecular targeted agents with  $t_{1/2} > 10$  days; 10 weeks for radio- or toxin-immunoconjugates); concurrent use of hormone deprivation therapy including but not limited to anastrozole, letrozole, or tamoxifen citrate for breast cancer and hormonal replacement therapy for non-cancer related conditions is permitted. Enrollment of subjects that have received molecularly-targeted small molecule inhibitors less than 21 days prior to study Day 1 will be permitted if more than 14 days and at least 5 drug half-lives have passed prior to receiving the first dose of ibrutinib.
4. Prior treatment with ibrutinib or other BTK inhibitor, anti-CD137 or anti-cytotoxic T-lymphocyte associated antigen 4 (CTLA-4) antibody. The following are exceptions to this criterion:
  - Subjects previously treated with anti-PD1, anti-PD-L1, or anti-PD-L2 antibody
5. Known allergy or hypersensitivity to ibrutinib or MEDI4736 or any excipients
6. Current or prior use of immunosuppressive medication within 14 days before the first dose of MEDI4736. The following are exceptions to this criterion:
  - Intranasal, inhaled, topical corticosteroids, or local corticosteroid injections (eg, intra-articular injection)

- Systemic corticosteroids at doses not to exceed 10 mg/day of prednisone or its equivalent
- Corticosteroids as pre-medication for hypersensitivity reactions (eg, CT scan pre-medication).

7. Active or prior documented autoimmune or inflammatory disorders (including but not limited to inflammatory bowel disease [eg, colitis, Crohn's disease], diverticulitis with the exception of a prior resolved episode or diverticulosis, celiac disease, irritable bowel disease, or other serious gastrointestinal chronic conditions associated with diarrhea; type 1 diabetes mellitus; multiple sclerosis; systemic lupus erythematosus; Wegener's granulomatosis; myasthenia gravis; Graves' disease; rheumatoid arthritis; hypophysitis; uveitis; etc) within the past 3 years prior to the start of treatment. The following are exceptions to this criterion:

- Subjects with vitiligo or alopecia
- Subjects with hypothyroidism (eg, following Hashimoto's thyroiditis) stable on hormone replacement therapy or psoriasis not requiring systemic treatment

8. History of allogeneic organ transplant

9. History of other malignancies, except

- Malignancy treated with curative intent and with no known active disease present for  $\geq 5$  years before the first dose of study drug and felt to be at low risk for recurrence by the treating physician
- Adequately treated non-melanoma skin cancer or lentigo maligna without evidence of disease
- Adequately treated carcinoma in situ without evidence of disease

10. Unresolved toxicities from prior anti-cancer therapy, defined as having not resolved to **CTCAE (v 4.03)**, Grade 0 or 1, or to the levels dictated in the inclusion/exclusion criteria with the exception of stable neuropathy, vitiligo and alopecia or other irreversible toxicity not reasonably expected to be exacerbated by study treatment (eg, hearing loss)

11. Known bleeding disorders (eg, von Willebrand's disease) or hemophilia

12. History of stroke or intracranial hemorrhage within 6 months prior to enrollment

13. Vaccinated with live, attenuated vaccines within 4 weeks of the first dose of study drug  
(Note: Subjects, if enrolled, should not receive live vaccines during the study and until 180 days after the last dose of study drugs)

14. Recent infection requiring systemic treatment that was completed  $\leq 14$  days before the first dose of study drug

15. Known history of human immunodeficiency virus (HIV) or active with hepatitis C virus (HCV) or hepatitis B virus (HBV).  
*Subjects who are positive for hepatitis B core antibody, hepatitis B surface antigen, or hepatitis C antibody must have a negative polymerase chain reaction (PCR) result before enrollment. Those who are PCR positive will be excluded.*

16. History of primary immunodeficiency

17. Known history of previous clinical diagnosis of tuberculosis
18. Any uncontrolled active systemic infection or pneumonitis or interstitial lung disease
19. Major surgery within 4 weeks of the first dose of study drug
20. Any life-threatening illness, medical condition, or organ system dysfunction that, in the investigator's opinion, could compromise the subject's safety or put the study outcomes at undue risk, eg psychiatric illness/social situations that would limit compliance with study requirement or compromise the ability of the subject to give written informed consent.
21. Currently active, clinically significant cardiovascular disease, such as uncontrolled arrhythmia or Class 3 or 4 congestive heart failure as defined by the New York Heart Association Functional Classification; or a history of myocardial infarction, uncontrolled hypertension or cardiac arrhythmia, unstable angina, or acute coronary syndrome within 6 months prior to enrollment ([Appendix 6](#))
22. Unable to swallow capsules or active malabsorption syndrome not controlled by medication, disease or conditions significantly affecting gastrointestinal function, or complete resection of the stomach, or complete resection of small bowel, or partial or complete bowel obstruction
23. Concomitant use of warfarin or other Vitamin K antagonists
24. Treatment with a strong CYP3A inhibitor ([Appendix 5](#))
25. Pregnant or lactating female; men planning to father a child or women planning a pregnancy while taking study drug or within 3 months after the last dose of study drug
26. Concurrent enrollment in another clinical study, unless in a follow-up period or it is an observational study.
27. Unwilling or unable to participate in all required study evaluations and procedures
28. Unable to understand the purpose and risks of the study and to provide a signed and dated informed consent form (ICF) and authorization to use protected health information (in accordance with national and local subject privacy regulations)

## **5. TREATMENT OF SUBJECTS**

### **5.1. Treatment Allocation**

This is an open-label study (both Phase 1b and Phase 2). After the subject has completed all baseline (screening) procedures and met all requirements of the inclusion/exclusion criteria, study site personnel can enroll the subject. All enrolled subjects will receive open-label ibrutinib capsules and MEDI4736.

Two dose levels of ibrutinib (560 or 420 mg/day) and MEDI4736 (10 or 3 mg/kg IV Q2 weeks) may be tested ([Table 1](#)). The starting dose will be 560 mg of ibrutinib PO daily and 10 mg/kg of MEDI4736 IV Q2 weeks. The dose may be modified based on the number of DLTs observed.

In each cohort, a sentinel subject will have a 3-day observation period prior to dosing of subsequent subjects to monitor for unexpected acute toxicities.

**Phase 1b:**

Subjects will be enrolled in up to 4 dose cohorts (1, -[minus]1A, -1B, or -2) regardless of tumor type (for dose levels see [Table 1](#)). Assignment of subjects to the two parallel dose de-escalation cohorts (-1A and -1B) will be concurrent and in the sequence of -1A followed by -1B. However, when one dose de-escalation cohort needs additional 3 subjects to evaluate DLTs, all available subjects will be assigned to this cohort first. If necessary, the dose de-escalation cohort -2 will be enrolled thereafter.

**Phase 2:**

Subjects will be treated at the RP2D as determined in Phase 1b. There will be no stratification of subjects within the pancreatic tumor type cohort. However, in the NSCLC cohort, subjects with adenocarcinoma or squamous-cell carcinoma will be enrolled at an approximate 2:1 ratio (ie, at least 15 subjects with squamous-cell carcinoma will be enrolled). In the breast cancer cohort, subjects with triple-negative or HER2-positive breast cancer will be enrolled at an approximate 2:1 ratio (ie, 15 subjects with triple-negative breast cancer will be enrolled).

## **5.2. Phase 1b Dose De-escalation and Stopping Rules**

Phase 1b will follow a 6+3 design with 6–9 subjects at each dose level. Before determining the RP2D, 6 subjects in any given cohort must have completed the DLT observation period, which is defined as the first 28 days of therapy. The DLT observation period includes Cycle 1 and laboratory assessments on Day 1 of Cycle 2 which will occur before the MEDI4736 infusion on Day 1 of Cycle 2. The dose will be selected as the RP2D if the subject incidence of DLTs during the first 28 days (Cycle 1=28 days and including laboratory assessments on Day 1 Cycle 2) of study treatment is <33% (ie,  $\leq 1/6$  or  $\leq 2/9$  subjects with a DLT). If there are  $\geq 3$  subjects with a DLT in Cohort 1, then the next lower dose level (Cohorts -1A and -1B, see [Table 1](#)) will be enrolled.

Cohorts -1A and -1B are two parallel dose de-escalation cohorts and will be enrolled concurrently in a non-randomized fashion in the sequence of -1A followed by -1B. For example, the first available subject will go to Cohort -1A, the second subject to Cohort -1B, the third to -1A, the fourth to -1B, etc. However, when one dose de-escalation cohort needs additional 3 subjects to evaluate DLTs, all available subjects will be assigned to this cohort first. In these cohorts, it will be determined which dosing schedule is most appropriate for the phase 2 portion of the study. Determination will be based on the safety profile of the 2 treatment regimens, potentially taking pharmacokinetics and pharmacodynamics aspects into consideration. If necessary, the dose de-escalation cohort -2 will be enrolled thereafter.

Enrollment in a cohort will proceed as follows:

- If 0 or 1 DLT is observed during the DLT observation period in the initial 6 subjects in Cohort 1, then this dose will be the RP2D.
- If 2 DLTs are observed in the initial 6 subjects in Cohort 1, then 3 additional subjects will be enrolled to this cohort.
  - If 0 DLT in the 3 additional subjects is observed, then this dose will be the RP2D.
  - If 1 or more DLT is observed, the dose will be de-escalated to Cohorts -1A and -1B
- If 3 or more DLTs are observed in the initial 6 subjects, then Cohort 1 will be stopped and the dose will be de-escalated to Cohorts -1A and -1B.

A similar 6+3 cohort design will be utilized in the dose de-escalation cohorts.

If a subject experiences a DLT during the DLT observation period, the subject will discontinue treatment. However, any subject(s) tolerating the dose level through the DLT observation period will continue to receive the same dose of study drugs even if a dose de-escalation occurs for other study subjects.

A Dose Level Review Committee (DLRC) will evaluate the safety data from each cohort of the Phase 1b. Members of this committee will include participating investigators or designees as well as the Sponsor (at a minimum: the Medical Monitor or designee, a Drug Safety representative and a Biostatistician).

### **5.3. Definition of Dose-Limiting Toxicity (DLT)**

The assessment of DLT will follow the guidelines provided in the [CTCAE v 4.03](#). A DLT is defined as any Grade 3 or higher non-hematologic or Grade 4 hematologic AE possibly related to study drug(s) occurring during the DLT observation period with the following clarifications for the toxicities below:

- Grade 4 vomiting or Grade 3 nausea and vomiting despite maximum medical supportive care and persisting >3 days
- Grade 3 or 4 diarrhea despite maximum medical supportive care and persisting >7 days
- Grade 3 fatigue persisting >7 days
- Grade 3 neutropenia lasting >7 days or with fever
- Grade 3 infusion reaction that does NOT resolve with appropriate clinical management

During the Phase 1b DLT observation period, subjects will be replaced for any of the following reasons:

- Missed >4 consecutive doses or missed 7 total doses of ibrutinib.
- Missed dose of MEDI4736 or received the MEDI4736 dose outside of the protocol-allowed window ( $\pm 2$  days).

- Study drug discontinuation for any reason other than DLT (ie, including PD).

Subjects who are replaced for missed doses may continue to receive study treatment if there is a clinical benefit and will be followed for response assessment and overall survival, but they will not be part of the DLT analysis.

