#### **5.5.2.2. Dose and Administration**

The liquid product is to be diluted with 0.9% saline for IV infusion.

The first dose will be administered in the clinic on Day 1 and then every 2 weeks thereafter for up to 12 months, regardless of any dose delays or missed doses.

MEDI4736 will be administered as an IV infusion approximately 1 hour in duration (including the IV line flush). The MEDI4736 dose will be calculated using the subject's weight at baseline. This dose should be used for each MEDI4736 administration, unless there is a >10% weight change. In the case of a >10% weight change, the weight at the MEDI4736 dose administration visit should be used to calculate the dose.

Following preparation of MEDI4736, the entire contents of the IV bag should be administered as an IV infusion over approximately 60 minutes ( $\pm$ 5 minutes), using a 0.2- $\mu$ m in-line filter. The IV line will be flushed with a volume of normal saline equal to the priming volume of the infusion set used after the contents of the IV bag are fully administered, or complete the infusion according to institutional policy to ensure the full dose is administered and document if the line

was not flushed. Since the compatibility of MEDI4736 with other IV medications and solutions, other than normal saline (0.9% [weight/volume] sodium chloride for injection), is not known, the MEDI4736 solution should not be infused through an IV line in which other solutions or medications are being administered. The ibrutinib dose should be given within 15 minutes after the end of the MEDI4736 infusion.

Subjects will be monitored during and after the infusion with assessment of vital signs at the times specified in the Schedule of Assessments. In the event of a Grade  $\leq 2$  infusion-related reaction, the infusion rate of study drug may be decreased by 50% or interrupted until resolution of the event (up to 4 hours) and re-initiated at 50% of the initial rate until completion of the infusion. For subjects with a Grade  $\leq 2$  infusion-related reaction, subsequent infusions may be administered at 50% of the initial rate. Acetaminophen and/or an antihistamine (eg, diphenhydramine), steroids, or equivalent medications per institutional standard may be administered at the discretion of the investigator. If the infusion-related reaction is Grade  $\geq 3$  in severity, study drug will be discontinued.

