#### **5.5.2.4. Dose Modification for Adverse Reactions**

Refer to [Section 6.1](#) for use of corticosteroids as concomitant medications.

The table below outlines the MEDI4736 Toxicity Management Guidelines.

Immune-Mediated Reactions		
	Dose Modifications	Toxicity Management
Immune-related Adverse Events (Overall Management for toxicities not noted below)	
Drug administration modifications of study drug/study regimen will be made to manage potential immune-related AEs based on severity of treatment-emergent toxicities graded per NCI CTCAE v4.03.
 
In addition to the criteria for permanent discontinuation of study drug/regimen based on CTC grade/severity (table below), permanently discontinue study drug/study regimen for the following conditions:
 
 
• Inability to reduce corticosteroid to a dose of <math>\leq 10</math> mg of prednisone per day (or equivalent) within 12 weeks after last dose of study drug/regimen
 
• Recurrence of a previously experienced Grade 3 treatment-related AE following resumption of dosing.
 
	
It is recommended that management of irAEs follow the guidelines presented in this Table:
 
 
• Subjects should be thoroughly evaluated to rule out any alternative etiology (eg, disease progression, concomitant medications, infections, etc.)
 
• In the absence of a clear alternative etiology, all events should be considered potentially immune related.
 
• Symptomatic and topical therapy should be considered for low-grade (Grade 1 or 2, unless otherwise specified) events
 
• For persistent (greater than 3 to 5 days) low-grade (Grade 2) or severe (Grade <math>\geq 3</math>) events promptly start prednisone PO 1-2mg/kg/day or IV equivalent
 
• If symptoms recur or worsen during corticosteroid tapering (28 days of taper), increase the corticosteroid dose (prednisone dose [eg, up to 2-4 mg/kg/day or IV equivalent]) until stabilization or improvement of symptoms, then resume corticosteroid tapering at a slower rate (<math>\geq 28</math> days of taper)
 
• More potent immunosuppressives – TNF inhibitors (eg, infliximab) – (also refer to the individual sections of the immune related adverse event for specific type of immunosuppressive) should be considered for events not responding to systemic steroids
 
• Discontinuation of study drug is not mandated for Grade 3/Grade 4 inflammatory reactions attributed to local tumour response (eg, inflammatory reaction at sites of metastatic disease, lymph nodes etc.). Continuation of study drug in this situation should be based upon a benefit/risk analysis for that subject.
 

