 ASCO Educational Book 2015 Michael Postow MD "Managing Immune Checkpoint Blocking Antibody Side Effects

Immune-Mediated Reactions			
	Dose Modifications		Toxicity Management
	Grade 3 or 4 diarrhea  (Grade 3: stool frequency of $\geq 7$ over baseline per day;  Grade 4: life threatening consequences)	Permanently discontinue study drug/study regimen	
For Grade 3 or 4 diarrhea:
 
 
Promptly initiate empiric IV methylprednisolone 2 to 4 mg/kg/day or equivalent
 
Monitor stool frequency and volume and maintain hydration
 
Urgent GI consult and imaging and/or colonoscopy as appropriate
 
If still no improvement within 3-5 days of IV methylprednisolone 2 to 4 mg/kg/day or equivalent, promptly start further immunosuppressives (eg, infliximab at 5mg/kg once every 2 weeks)
 
Caution: Ensure GI consult to rule out perforation and refer to infliximab label for general guidance before using infliximab.
 
Once improving, gradually taper steroids over <math>\geq 28</math> days and consider prophylactic antibiotics, antifungals and anti PCP treatment (please refer to current NCCN guidelines for treatment of cancer-related infections [Category 2B recommendation])
 

Hepatitis  (Elevated LFTs)  Infliximab should not be used for management of Immune Related Hepatitis	Grade of Liver Function Test Elevation  (CTCAE v 4.03)  Any Grade		
 
Monitor and evaluate liver function test: AST, ALT, ALP and total bilirubin
 
Evaluate for alternative etiologies (eg, viral hepatitis, disease progression, concomitant medications)
 

	Grade 1  (AST or ALT $>$ ULN to 3 times ULN and/or TB $>$ ULN to 1.5 times ULN)	No dose modification  If it worsens, treat as Grade 2 event	
For Grade 1 AST or ALT and/or TB elevation
 
 
Continue LFT monitoring per protocol
 

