3	Hold study drug/study regimen until resolution to Grade $\leq 1$ or baseline For AEs that downgrade to Grade $\leq 2$ within 7 days or resolve to Grade $\leq 1$ or baseline within 14 days, resume study drug/study regimen administration at next scheduled dose. Otherwise, discontinue study drug/study regimen	Treat accordingly as per institutional standard
4	Discontinue Study drug/study regimen (Note for Grade 4 labs, decision to discontinue would be based on accompanying clinical signs/symptoms and as per Investigator's clinical judgment and in consultation with the sponsor)	Treat accordingly as per institutional standard

Abbreviations:

AChE = acetylcholine esterase; ADA = American Dietetic Association; AE = adverse event; ALP = alkaline phosphatase; ALT = alanine aminotransferase; AST = aspartate aminotransferase; CT = computed tomography; GI = gastrointestinal; IDS=Infectious Disease Service; ILD = interstitial lung disease; IM = intramuscular; irAE = immune- related adverse event; IV = intravenous; NCI CTCAE = National Cancer Institute Common Terminology Criteria for Adverse Events; PO = by mouth; TNF = tumor necrosis factor; TSH = thyroid stimulating hormone; ULN = upper limit of normal.

i ASCO Educational Book 2015 "Managing Immune Checkpoint Blocking Antibody Side Effects" by Michael Postow MD

ii NCI CTCAE v4.03

iii ASCO Educational Book 2015 "Managing Immune Checkpoint Blocking Antibody Side Effects" by Michael Postow MD

iv FDA Liver Guidance Document 2009 Guidance for Industry: Drug Induced Liver Injury – Premarketing Clinical Evaluation

MEDI4736 treatment interruptions in study drug administration should be recorded in the clinical database.

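### Phase 1b replaces a subject whose related Grade 3/4 diarrhea ends treatment within 7 days, so the event drops out of the RP2D count; the average effect is small and the fix is wording

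*Protocol*

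**What the plan says.** **DLT definition (Protocol 5.3).** Possibly related non-hematologic events of Grade 3 or higher count, subject to clarifications. Two matter here: "Grade 3 or 4 diarrhea despite maximum medical supportive care and persisting >7 days" and "Grade 3 infusion reaction that does NOT resolve with appropriate clinical management".

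**Stopping rules (Protocol 5.5).** For Grade 3 or 4 diarrhea, the immune-mediated table in 5.5.2.4 says "Permanently discontinue study drug/study regimen", with no duration condition. That table is the default: "In the absence of a clear alternative etiology, all events should be considered potentially immune related". The non-immune table in the same section also discontinues for Grade 4 events generally. For infusion reactions of Grade 3 or higher, 5.5.2.2 says "in severity, study drug will be discontinued", whether or not the reaction resolves. The infusion-reaction table in 5.5.2.4 agrees, and Section 11.4.6.3 stops MEDI4736.

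**Replacement (Protocol 5.3).** During the DLT period subjects are replaced for "Study drug discontinuation for any reason other than DLT (ie, including PD", for "Missed >4 consecutive doses or missed 7 total doses of ibrutinib", and for a missed or out-of-window MEDI4736 dose. The synopsis repeats the discontinuation rule. SAP 2.1 restricts the DLT Evaluable Population to subjects who did not meet the replacement criteria.

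**Decision rule (Protocol 5.2).** A dose is accepted with 0 or 1 DLT in 6, or with 2 in 6 followed by none in 3 more.

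**The concern.** The replacement rule makes no exception for toxicity. Diarrhea that is related, Grade 3 or 4, managed as immune-mediated, over within 7 days and not diagnosed as colitis is too severe for that subject to continue, yet it is not a DLT. The subject has stopped for a reason other than DLT and is swapped for a new one. The same holds for related Grade 4 diarrhea of 7 days or less that is stopped under the non-immune table.

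Replacement is harmless when the reason is unrelated to the drugs, such as progression. Here the reason is drug toxicity, so the count is biased toward accepting the dose. A duration limit on diarrhea makes sense if the subject can recover and resume. It loses that rationale where another section forbids resuming.

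This matters because Phase 1b exists to find overlapping toxicity. Section 1.4.4.4 calls diarrhea the most frequent non-hematologic event with ibrutinib, while noting that gastrointestinal events were rarely severe. Section 1.5.3 lists diarrhea among the related events of durvalumab, including at Grade 4. Section 1.4.5 reports no clinical data for the combination in these tumors.

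**Working it through.** **The plan's own figures.** One cohort of 6 gives 6 subjects and four cohorts of 9 give 36, matching the 6 to 36 in Protocol 10.4.1. The accepted fractions 1/6 = 16.7% and 2/9 = 22.2% lie below 33.3%; 2/6 and 3/9 do not. The rule reproduces.

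**What replacement does to the count.** Take 7 treated subjects: 1 with a DLT, 1 stopped and replaced for short Grade 3 diarrhea. The rule sees 1/6 and accepts, although 2/7 = 28.6% stopped for related toxicity. If both events fell in the first six and both counted, 2/6 would require three more subjects.

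**Inputs.** The documents give no rate for the combination. The single-agent rates below cover whole treatment courses, not 28 days.
- Durvalumab, related Grade 3 or higher diarrhea: not among the events seen in 3 or more of 694 subjects (Protocol 1.5.3), so at most 2/694 = 0.29%.
- Durvalumab, Grade 3 infusion reaction: 1 of 414 (Protocol 1.8.2) = 0.24%.
- Sum: q = 0.53%, assuming that the rates add and every case falls in the gap.
- Ibrutinib, Grade 3/4 diarrhea: absent from the lists of events above 2% (Protocol 1.4.3.1 and 1.4.3.2). This gives only a ceiling of 2%, and for all causes. Adding it gives q = 2.53%.
- DLT rate p: assumed, 10% to 30%.

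**Formula.** Let A(π) be the chance of accepting a dose when each counted subject has a DLT with probability π:

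A(π) = P(X₆ ≤ 1) + P(X₆ = 2) × (1 − π)³, with X₆ binomial (6, π).

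As written, affected subjects are replaced, so π = p/(1 − q). If their events counted, π = p + q.

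**Worked case, p = 15%, q = 0.53%.**
- As written: π = 0.15/0.9947 = 0.1508; A = 0.7746 + 0.1774 × 0.6124 = 0.8832.
- If counted: π = 0.1553; A = 0.7640 + 0.1842 × 0.6027 = 0.8750.
- Difference: 0.8 points.

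**Across DLT rates, q = 0.53%.**

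| DLT rate p | As written | If counted | Difference (points) |
|---|---|---|---|
| 10% | 0.9569 | 0.9515 | 0.5 |
| 15% | 0.8832 | 0.8750 | 0.8 |
| 20% | 0.7787 | 0.7689 | 1.0 |
| 25% | 0.6557 | 0.6456 | 1.0 |
| 30% | 0.5273 | 0.5180 | 0.9 |

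With diarrhea alone (q = 2/694) and p = 15%, the difference is 0.8839 − 0.8794, about 0.45 points.

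**Sensitivity.** With the ibrutinib ceiling (q = 2.53%) the difference is 3.0 to 4.8 points over the same DLT rates. At an assumed q of 5% and p = 15% it is 0.8701 − 0.7812 = 8.9 points.

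**Given that an event has happened.** The chance of at least one in six treated subjects is 1 − (1 − 0.0053)⁶ = 3.1%. Suppose exactly one occurs, with p = 15%. As written, acceptance stays at 0.883. If counted, the other five must have no DLT, or one DLT followed by a clean expansion:

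(1 − π)⁵ + 5π(1 − π)⁴ × (1 − p − q)³ = 0.4416 + 0.3921 × 0.6027 = 0.678.

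The difference is 20.5 points.

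**The case against.** **The diarrhea route is narrow.** A related Grade 3 colitis reported as such is a DLT under the general clause, with no duration limit, and Section 11.4.2 asks for a diagnosis rather than symptoms where possible. Grade 3 diarrhea with a clear non-immune cause may be held and resumed. This stands, and it limits the point to the cases named in the concern. The calculation puts every case in the gap, so the single-agent rates overstate the route.

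**The ibrutinib term is weak.** It supplies about four-fifths of the 2.53% (0.02/0.0253). It is inferred from absence from a list, and ibrutinib's own rules in 5.5.1.4 are to withhold and restart. This stands; the 3 to 5 point shifts are a sensitivity bound, not an estimate.

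**Resolving infusion reactions are excluded on purpose.** The wording in 5.3 is plainly deliberate, and Section 11.4.6.3 stops only MEDI4736. Both points stand. Losing MEDI4736 in the DLT period still leads to replacement, so the event still goes uncounted, but this half is a sponsor choice to make visible rather than a clear error.

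**The events stay visible.** The Dose Level Review Committee reviews each cohort's safety data (5.2 and 10.8), and Phase 2 has an interim safety review. That limits harm. However, nothing in those sections returns a replaced subject to the count.

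**The clarifications may only illustrate the general Grade 3 rule.** This does not stand: the 7-day and non-resolution conditions would then have no effect.

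**Conclusion.** The point holds on the text. Read together, the DLT definition, stopping rules and replacement rule remove some treatment-ending related toxicity from the count that sets the recommended dose. The direction does not depend on any assumed rate.

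The expected size is small: about 0.5 to 1 point in acceptance probability at q = 0.53% and DLT rates of 10% to 30%. This rests on single-agent, whole-course rates that are taken to add and to fall wholly in the gap. The combination's rate is unknown.

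A reader might infer three stronger things that the documents do not support:
- That the 6+3 rule is badly miscalibrated. The 20-point difference applies only once an event has occurred (about a 3% chance in six subjects at q = 0.53%), and a 9-point average shift needs an assumed 5% rate.
- That all severe diarrhea escapes the count. Longer episodes and diagnosed colitis remain DLTs.
- That a resolving Grade 3 infusion reaction certainly ends both drugs. Sections 5.5.2.2 and 5.5.2.4 can be read that way, but Section 11.4.6.3 names only MEDI4736.

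The change is still worth making: it is cheap, and the gap matters most in the cohort where such an event occurs.

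**What to change.** Make these changes in Protocol 5.3, the synopsis and SAP 2.1:
- Count as a DLT, regardless of duration, any possibly related non-hematologic toxicity of Grade 3 or higher in the DLT period that requires permanent discontinuation of ibrutinib or MEDI4736 under Section 5.5. The grade floor is needed: without it, the rule would also take in any bullous rash and Grade 2 neuromotor events with autonomic instability, which Section 5.5.2.4 can also stop.
- Limit replacement for discontinuation to reasons other than related toxicity, such as progression or withdrawal.
- If resolved Grade 3 infusion reactions are to stay outside the definition, name that exception and report those subjects beside the DLT count.
- Also report beside the count any subject replaced for doses missed because of related Grade 3 or 4 toxicity.
- In SAP 2.1, point to Protocol 5.3 for the replacement criteria. Its present reference, Section 1.4.1, is not in the supplied SAP text.

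The cost is wording only, with no new data. A cohort may slightly more often need its 3 extra subjects or de-escalate, within the planned maximum of 36. At a 15% DLT rate and q = 0.53%, the chance of accepting a dose falls by about 0.8 points.
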